# 5. Risks

a. Medical risks, listing all procedures, their major and minor risks and expected frequency.

Generally speaking there is minimal risk in participating in this study. If the patient is randomized to the standard of care they will receive our Centers standard of care for incisional wounds. If the patient is randomized to the Prevena incisional wound VAC system they may experience the following:

- 1. Discomfort and inability to tolerate the incisional wound VAC system: In this situation the dressing will be inspected by the Principle Investigator or wound nursing team who will ensure that the VAC system is properly placed and working correctly. In the event that the patient is still unable to tolerate the device, it will be removed and the patient will be excluded from the study.
- 2. Skin abrasion or irritation: If on inspection the skin edges at the incision appear to be red or irritated the incisional wound VAC will be removed and the incision inspected. The patient would be removed from the study.
- 3. Allergic reaction to the device: If at any time during the study the patient appears to have an allergic reaction to the incisional wound VAC device. The Principle Investigator will determine if the dressing needs to be removed and the patient will be removed from the study.Redness or erythema, fever, signs of infection: Should there be any concern for infection under the incisional wound VAC, it will be removed immediately and the incision assessed by the Principle Investigator, Nurse Practitioner or Physician Assistant. Appropriate standard of care will be initiated should the wound indeed be infected. This may include opening and draining the incision, wet to dry dressing changes and antibiotics treatment.
  - b. Steps taken to minimize the risks.

Follow standard surgical procedures and placement of wound dressing or Prevena Wound VAC.

c. Plan for reporting unanticipated problems or study deviations.

All events will be reported to the JHM IRB as required by the JHM IRB reporting guidelines posted on the JHM IRB website.

d. Legal risks such as the risks that would be associated with breach of confidentiality.

There should be no legal risks by participating in this study. None beyond those associated with routine care.

e. Financial risks to the participants.

None beyond those associated with routine care.

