**Potential Problems and Alternative Strategies:** We acknowledge that the patient may not tolerate the Prevena dressing (patient adherence) – though we received very positive results from patients we piloted Prevena on and many say that they like the way it feels. However, if at any time a patient develops an allergic reaction or is unable to tolerate the Prevena dressing (such as severe incision site skin irritation or discomfort) it will be replaced by standard gauze dressing and the patient's hypersensitive reaction will be treated according to best medical management. In such case of crossover between the two treatment groups a sensitivity analysis will be performed to decide whether the number of crossover cases will have a significant effect on the outcome of the study. However, all protocol deviation cases and secondary outcomes will be reported in our final paper.

c. Blinding, including justification for blinding or not blinding the trial, if applicable.

This is a prospective single blinded randomized clinical trial. It is blinded in order to minimize any potential bias the participants may have for or against the new Prevena in comparison to the standard of care dressing.

d. Justification of why participants will not receive routine care or will have current therapy stopped.

All participants will receive routine care and will not have current therapy stopped.

e. Justification for inclusion of a placebo or non-treatment group. Not applicable

f. Definition of treatment failure or participant removal criteria.

In case of intolerance or development of an allergic reaction (such as severe incision site skin irritation or discomfort) it will be replaced by standard gauze dressing and the patient's hypersensitive reaction will be treated according to best medical practice.

g. Description of what happens to participants receiving therapy when study ends or if a participant's participation in the study ends prematurely. **Not applicable** 

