# b. Secondary outcome variables:

- 1. Other wound complications (such as dehiscence, seroma and hematoma)
- 2. Skin bacterial count after treatment

- 3. Wound healing time
- 4. Quality of life scores (SF-36 or VQL)
- c. Statistical plan including sample size justification and interim data analysis.

Power and sample size were calculated using SamplePower 2, alpha set at .05, and power of at least 80%. Current literature values suggest a similar SSI rate of 17-24%.(14, 15)

The use of Prevena has been tested in a small retrospective study (52 Prevena devices) of groin incisions in vascular surgery that yielded a large difference of 24% in SSI rates (Prevena 6%, Non-Prevena 30%).(15) Another retrospective study of Prevena use in plastic surgery showed a difference of 17% in SSI rates in patient groups receiving skin grafts (Prevena 3%, Non-Prevena 20%).(14) However, to this date the use of Prevena has not been documented in obese patients.

For a difference of 24% between control and Prevena groups, 27 patients per group (N=54) are needed to achieve power of 80%. Decreasing the group difference to 20% requires 39 patients per group (N=78) for power of at least 80%. Decreasing the group difference even further to 17% requires 54 patients per group (N=108) for power of at least 80%. To detect a smallest difference of 17%, we estimated the need for a total of 108 patients to be enrolled in this study.

- d. Early stopping rules.
  - 1. Inability to tolerate the Prevena Wound VAC
  - 2. Allergic reaction to the Prevena Wound VAC
  - 3. Evidence of wound infection during the use of Prevena Wound VAC
  - 4. Fever of >38.0 during the time the Prevena Wound VAC is in place (the wound VAC should be removed and infection of the skin ruled out)
  - 5. Statistical evidence that the Prevena Wound VAC has better outcomes versus the standard of care wound dressing\*

\*we will carry out a review of the outcomes every 6 months in this study

In order to alleviate the possibility of diabetes and smoking influencing a patient's wound healing outcomes, we stratified our randomization groups into 4 strata:

- 1) Diabetic Smoker
- 2) Diabetic Non-smoker
- 3) Non-diabetic Smoker
- 4) Non-diabetic non-smoker

Given our sample size we ran the randomization schemes for up to 60 patients in each strata.

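### Section 5 removes randomised patients from the study in the Prevena arm only, contradicts the crossover rule, and may take infections out of one arm of the primary comparison

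*Combined protocol and SAP*

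**What the plan says.** The Enrollment text counts a patient as enrolled once randomised. Section 5, part a, then lists what may happen to patients randomised to Prevena:

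- **Item 1, intolerance:** if it persists after the device is checked, "it will be removed and the patient will be excluded from the study".
- **Item 2, skin abrasion or irritation:** if "the skin edges at the incision appear to be red or irritated the incisional wound VAC will be removed and the incision inspected", the consequence is "The patient would be removed from the study".
- **Item 3, allergic reaction:** the investigator decides whether "the dressing needs to be removed and the patient will be removed from the study".
- **Redness, fever or signs of infection** (run on after item 3): "Should there be any concern for infection under the incisional wound VAC, it will be removed immediately and the incision assessed". Treatment follows if the wound is infected. Leaving the study is not mentioned.

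No such rule is given for the standard-dressing arm.

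Section 1 (Potential Problems and Alternative Strategies) handles intolerance, allergy and severe skin irritation by replacing Prevena with gauze, and adds: "In such case of crossover between the two treatment groups a sensitivity analysis will be performed". Item f of that section, headed "Definition of treatment failure or participant removal criteria", states only the dressing replacement. Section 1, item b, follows each participant through POD 30-35.

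Section 4, item d, lists four Prevena-specific early stopping rules, the first being "Inability to tolerate the Prevena Wound VAC", without saying what they mean for follow-up or analysis. Section 4, item c, defines no analysis population.

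**The concern.** The exclusions act after randomisation and in one arm, so the patients left in the two arms are no longer those that randomisation made comparable. One trigger also overlaps with the primary outcome. Redness prompts early dressing removal in both arms (Postoperative wound management), is a warning sign given to patients (Follow Up), and opens the infection text in Section 5. It is also the trigger for item 2. A red Prevena incision can therefore lead either to removal from the study or to an infection assessment, while a red control incision has only the second route. If some item 2 patients have an early SSI, those events are lost from the Prevena arm alone and the comparison leans towards Prevena. Items 1 and 3 have no documented link to SSI.

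Separately, two teams following Section 1 and Section 5 would analyse different sets of patients.

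**Working it through.** **Passages side by side**

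| Event under Prevena | Section 5, part a | Section 1 |
|---|---|---|
| Intolerance | Out of the study | Gauze; crossover; sensitivity analysis |
| Skin irritation | Out of the study (red or irritated edges) | Gauze; crossover (severe irritation) |
| Allergy | Out of the study | Gauze; crossover; sensitivity analysis |
| Suspected infection | Device off, assess, treat | Dressing off early, swab, assess (both arms) |

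The first three rows conflict. A crossover sensitivity analysis needs the outcomes of the patients that Section 5 takes out.

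**Inputs from Section 4, item c:** alpha 0.05 (two-sided assumed), power 80%, SSI 20% against 3%, 54 per group, no allowance for removals.

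**The plan's own figure.** Pooled two-proportion formula, with mean proportion 0.115:

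n = [1.960 × √(2 × 0.115 × 0.885) + 0.842 × √(0.20 × 0.80 + 0.03 × 0.97)]² / 0.17² = 54.1, so 55 per group. At 54 the power is 79.9%. The stated 54 reproduces to within one patient.

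**Few events carry the result.** Expected infections are 54 × 0.20 = 10.8 in control and 54 × 0.03 = 1.6 under Prevena. As an illustration, 11/54 against 4/54 gives p = 0.051 (chi-square) or 0.093 (Fisher). Removing two of the four infected Prevena patients gives 11/54 against 2/52, p = 0.0095 or 0.015.

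**False findings in favour of Prevena.** Assume no true effect and SSI risk p = 0.20 in both arms. Of 54 Prevena patients, k are removed, with SSI risk r among them. Those who remain have risk

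q = (54p − kr) / (54 − k),

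so the arm average stays at p. For example, k = 5 and r = 0.50 gives q = (10.8 − 2.5)/49 = 16.9%. Exact binomial enumeration of the pooled z-test, counting only rejections that favour Prevena (nominal 2.5%), gives, with q in brackets:

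| SSI risk among those removed | k = 3 | k = 5 | k = 8 |
|---|---|---|---|
| 20% (average) | 2.6% (20.0%) | 2.5% (20.0%) | 2.5% (20.0%) |
| 30% | 3.0% | 3.3% | 4.1% |
| 50% | 4.2% (18.2%) | 5.8% (16.9%) | 10.1% (14.8%) |
| 80% | 6.8% (16.5%) | 12.7% (13.9%) | 31.9% (9.6%) |

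With p = 0.15, the 50% row becomes 4.9%, 7.6% and 16.2%.

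**Bounding case.** If only infected Prevena patients are dropped (p = 0.20), losing 10%, 25%, 50% or 75% of the arm's infections gives 4.0%, 8.0%, 23% or 56%. The 10% case falls to 3.6% if 2.5% of uninfected Prevena patients are dropped too.

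**Removal unrelated to infection.** Only power is lost: from 79.9% to 78.6%, 77.1% or 73.5% when 5%, 10% or 20% of the Prevena arm is removed.

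**The case against.** The strongest reply is that Section 5 separates irritation from infection. Item 2 is headed as abrasion or irritation, and the infection text sends any suspected infection to assessment without removing the patient. Read that way, infections stay in the study and the shared word for redness is loose drafting. No passage says that infected patients are dropped.

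The larger figures also assume a great deal. Eight removals is 15% of the arm, and at 80% risk they take out 8 × 0.80 = 6.4 of 10.8 expected infections, or 59%. The plan names no primary test. Fisher's exact test gives lower rates: 2.2%, 2.5% and 3.1% at 30% risk, and 3.1%, 4.6% and 7.7% at 50%. Section 1 also promises to report all protocol deviations. The POD 30-35 sentence and the early stopping list are weaker conflicts: a removed patient may no longer count as a participant, and the list is silent rather than contradictory.

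Much of this stands as a limit on size. The route to lost infections is item 2 alone, it is conditional, and the upper figures are bounds rather than forecasts. Fisher's test is conservative, so its own starting point is below 2.5%, and it does not remove the bias. The direct contradiction between Section 1 and Section 5 remains, as does the absence of an as-randomised analysis. Reporting deviations does not recover outcomes that were never collected.

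**Conclusion.** The concern holds and must be fixed. As written, Section 5 makes one-arm, post-randomisation exclusions that contradict Section 1, and nothing in the statistical plan says which patients enter the primary analysis. That conclusion needs no assumption.

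The bias is possible rather than demonstrated, and its size cannot be fixed from the documents. Assuming 20% SSI in both arms, 54 per arm and a pooled z-test, the false rate in favour of Prevena stays near 2.5% if those removed have average SSI risk. It rises to 3.0%-4.1% at 30% risk and 4.2%-10.1% at 50% risk for three to eight removals. The higher figures apply only if most of those removed are infected.

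**What to change.** Reconcile Section 1 (Potential Problems and item f), Section 4 item d (rules 1-4) and Section 5 part a (items 1-3) with one statement, for example: *A participant whose study dressing is stopped or replaced stays in the study and completes all scheduled assessments through POD 30-35, unless consent is withdrawn.* Delete the words in Section 5 that exclude or remove such patients from the study.

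Add to Section 4, item c: *The primary analysis includes every randomised patient in the assigned arm and counts any SSI, whatever dressing is in place.* Keep the crossover analysis as a sensitivity analysis, and report dressing stops and their reasons by arm. When and why a dressing is removed is left unchanged.

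The cost is protocol wording and a few more patients completing visits that are already scheduled. The estimated effect may be smaller, because patients who stop the device count in the Prevena arm; by how much depends on their number and SSI risk.

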**Hypothesis 2A:** Obese patients who have the Prevena system applied to their incision will have a lower bacterial skin count upon removing Prevena on post-operative day #5-7 as compared to those who had a standard of care dressing placed.

**Specific Aim 3:** To determine whether obese patients who have incisional wound PrevenaTM applied during their surgical procedure have better quality of life assessment as compared to those obese patients who have a standard of care dressing.

**Hypothesis 3A:** Obese patients who have the Prevena system applied to their incision will experience less wound complications and improved quality of life scores using the SF-36 (appendix A).

**Specific Aim 4:** To determine whether obese patients who have an incisional wound PrevenaTM applied during their surgical procedure have decreased readmission rates compared to those obese patients who have a standard of care dressing.

**Hypothesis 4A:** Obese patients who have the Prevena system applied to their incision will experience a decreased readmission rate within 30 days of the operation.

**The primary outcome measure:** the incidence of postoperative surgical site infection (according to CDC/NHSN protocol) in open surgery.

**The secondary outcome measures:** other wound complications (such as dehiscence, seroma and hematoma), skin bacterial count after treatment, wound healing time, quality of life reporting and readmission rates between the two groups.

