# Postoperative wound management

As it will be stated and agreed upon in the informed consent, the dressings in both groups will be removed on post-operative day(POD) # 5-7 (or sooner if redness or signs of infection are noted), by the provider/research coordinator in the clinic or on the ward if they are an inpatient. Then the provider/research coordinator will repeat the swabbing procedure mentioned above. Once swabbing is complete, an NP or a PA who are blinded to the study, will come in and asses the wound for healing, infection and other complications.

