# Follow Up

The patient will be advised to contact the hospital if any of the following signs develop at any time after the procedure (before and in between follow ups):

- a. Fever
- b. Warm, red, painful, swollen wound
- c. Blood or pus coming from the wound
- d. Foul odor coming from the wound

- 1) **POD #1-2:** The patient will receive a personal interview within 24-48 hours of the surgery while still hospitalized by an RN. A Short-Term Prevena Recovery Questionnaire (appendix B) will be completed during the interview regarding the patient's recovery. The most important questions will be tailored towards identifying any allergic reaction symptoms to the treatment option. Other questions include: tolerance, nutrition habits, voiding and bowel movements and any signs of wound infection.
- 2) **POD #5-7:** An examination by an independent nurse practitioner or physician assistant who is blinded to the treatment groups will be performed. Any surgical site infections or complications will be diagnosed using the Center for Disease Control and Prevention guidelines. If there are any complications (i.e. delayed healing, infection), the patient will be scheduled for weekly follow up with the NP, PA or MD until complete wound healing.
- 3) **POD #12 to 14:** Patients will return to clinic for staple or suture removal by the surgeon, the NP or PA. A secondary wound assessment will be performed as in step (2). In the same visit an SF-36 questionnaire (appendix A) will be completed by the patient to evaluate the therapy's impact on QOL.
- 4) POD # 30± 5 days: The patient will receive a phone call or personal interview (if still hospitalized) from one of our team members. A Long-Term Prevena Recovery Questionnaire (appendix C) will be completed during the calls regarding the patient's recovery. Questions about any possible wound complications include: incision check-up (changes in wound appearance and any of the signs mentioned above), development of any new symptom (fever, bowel habit changes, and nutrition habits).

Note: This time frame for follow up was chosen because:

- a. It will minimize data lost to follow up.
- b. It will maximize the opportunity for detection of infection, since the majority of SSIs are apparent by postoperative day 3-5.
- c. The standard of care at the Johns Hopkins surgical department includes a post-op check and visit 5 to 14 days following surgery.
- b. Study duration and number of study visits required of research participants.

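### The protocol gives two different rules for who judges a suspected infection at early dressing removal, one blinded and one (Prevena arm only) not, and does not say whose diagnosis counts for the primary outcome

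*Combined protocol and SAP*

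**What the plan says.** The Objectives section defines the primary outcome as "the incidence of postoperative surgical site infection (according to CDC/NHSN protocol) in open surgery".

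Assessors are named in several places:

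- **Postoperative wound management (both arms).** Dressings come off on POD 5-7, "or sooner if redness or signs of infection are noted". The provider or research coordinator removes the dressing and takes the swab; then "an NP or a PA who are blinded to the study, will come in and asses the wound".
- **Risks, a. Medical risks (Prevena arm only).** If there is concern for infection under the device, "it will be removed immediately and the incision assessed by the Principle Investigator, Nurse Practitioner or Physician Assistant". Blinding is not mentioned.
- **Follow Up, item 2 (POD 5-7).** "An examination by an independent nurse practitioner or physician assistant who is blinded to the treatment groups will be performed". If a complication is present, "the patient will be scheduled for weekly follow up with the NP, PA or MD until complete wound healing".
- **Follow Up, item 3 (POD 12-14).** "Patients will return to clinic for staple or suture removal by the surgeon, the NP or PA". The wound assessment at that visit is a separate sentence that refers back to step 2.
- **Follow Up, item 4 (POD 30 ± 5).** A team member makes contact by phone or, for inpatients, in person. Blinding is not stated.

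The Blinding paragraph (Study Procedures, c) calls the trial single blinded and gives one reason: "It is blinded in order to minimize any potential bias the participants may have". It does not mention outcome assessors. No adjudication is described, and nothing says whose diagnosis is used when more than one clinician has seen the wound.

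**The concern.** Suspected infection during dressing wear is one event with two assessor rules. Under the first, somebody else takes the dressing off and a blinded NP or PA then judges the wound. Under the second, the Principal Investigator may judge it, and nothing says that the assessor is blinded or arrives after removal. The second rule exists for one arm only, so following it as written would make the method of ascertainment depend on treatment.

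This matters because of timing. The rationale for the follow-up schedule says that most SSIs show by POD 3-5, whereas the scheduled blinded examination is at POD 5-7. On the protocol's own reasoning, early removal is a plausible route for primary-outcome events. The Innovations and Limitations text also shows that the investigators already regard the device favourably. Unblinded calls on doubtful wounds in one arm could shift a comparison that rests on few events.

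**Working it through.** **1. The two rules side by side**

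| | Postoperative wound management | Risks, a |
|---|---|---|
| Event | Early removal for redness or signs of infection | Concern for infection under the device |
| Arms | Both | Prevena only |
| Assessor | NP or PA | Principal Investigator, NP or PA |
| Blinded | Yes | Not stated |
| Sequence | Others remove and swab, then the assessor enters | Not stated |

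For a Prevena patient the two rows describe the same event. They agree only if the Risks assessor happens to be the blinded NP or PA.

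**2. The other contacts**

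- POD 12-14: the surgeon may remove the closures, but the assessment refers back to step 2, the blinded examination. No gap.
- Weekly visits: these start after a complication is found at the blinded POD 5-7 examination. An infection found there is already diagnosed blind. A gap remains only if an SSI develops later in a patient first flagged for something else.
- POD 30: the assessor's blinding is not stated. A small gap for late events.

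**3. The plan's own figures**

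Inputs from Study Statistics, c: 20% v 3%, alpha 0.05, power 80%, 54 per group. The sides of the test are not stated; two-sided is assumed. With p̄ = (0.20 + 0.03)/2 = 0.115:

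n = [1.960·√(2·0.115·0.885) + 0.8416·√(0.20·0.80 + 0.03·0.97)]² / 0.17² = (0.884 + 0.366)² / 0.0289 ≈ 54.1

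Rounded up this is 55, against 54 stated; power at 54 is 79.9%. The plan's figure reproduces.

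Expected SSIs are 54 × 0.20 = 10.8 and 54 × 0.03 = 1.6, about 12 in all. By an uncorrected Pearson test, 11 v 2 gives p = 0.008, 11 v 3 gives p = 0.022 and 11 v 4 gives p = 0.051. Two reclassified Prevena wounds are enough to cross the 0.05 line.

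**4. Illustration of the error rate (assumed values)**

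Assume no true effect, an SSI rate of 20% in both arms, and 54 per arm. Let f be the share of Prevena SSIs judged unblinded and m the fraction of those not called SSI. The recorded Prevena rate is 0.20 × (1 − f·m). The exact rejection probability sums the product of the two binomial probabilities over all tables with |z| > 1.96 (pooled, uncorrected). With no bias it is 5.1%.

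| m | f = 1: recorded rate, rejection | f = 0.5: recorded rate, rejection | f = 0.25: rejection |
|---|---|---|---|
| 10% | 18%, 5.9% | 19%, 5.3% | 5.1% |
| 20% | 16%, 8.4% | 18%, 5.9% | 5.3% |
| 30% | 14%, 13.0% | 17%, 6.9% | 5.5% |

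The chance of falsely favouring Prevena, 2.5% without bias, becomes 4.5%, 7.8% and 12.8% in the f = 1 column. The documents supply neither f nor m.

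**The case against.** The strongest reply is that the study-procedures text already covers early removal in both arms and sends the wound to a blinded assessor. The Risks paragraph can be read as safety management: it says who looks at the wound so that treatment can start, not who sets the trial endpoint. It also lists an NP and a PA, and nothing in it cancels the blinded assessment.

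Much of this stands. A reader might infer that blinding applies only at scheduled visits; the clause on earlier removal shows otherwise. A reader might also infer that the surgeon decides SSI status at POD 12-14, or that an MD does so at weekly visits. The first is contradicted by the reference back to step 2. The second is mostly excluded because the weekly visits follow a blinded finding.

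The direction of bias is also open. Extra scrutiny under the Risks paragraph, applied to one arm, could raise recorded Prevena SSIs and work against the device.

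What the reply does not remove is the conflict. If the Principal Investigator has assessed and treated a suspected infection, the protocol does not require a blinded assessment before that decision, and does not say which judgement is recorded as the outcome.

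**Conclusion.** The point holds in limited form. Postoperative wound management and Risks must be reconciled on who judges suspected infection under the dressing, because one route is blinded for both arms and the other is unblinded, or at least unspecified, for one arm only. The weekly visits and the POD 30 contact are smaller gaps of the same kind.

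It would go too far to say that many primary-outcome diagnoses fall outside the blind: the documents give no count or share, and if the study-procedures text governs, early suspected infections are seen by a blinded assessor too. **Some Prevena-arm diagnoses could be made unblinded** is as far as the text supports.

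The effect on error is modest unless most Prevena SSIs take the unblinded route: at most 6.9% two-sided rejection with half judged unblinded and up to 30% under-calling, against 13.0% if all are. These figures assume a true 20% rate in both arms, an uncorrected two-sided test and bias in the device's favour. With about 12 events expected, this should be corrected, but it does not undermine the design.

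**What to change.** State one rule in Study Procedures and cross-refer to it from Risks and from the Blinding paragraph:

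- For the primary analysis, SSI status at every wound assessment (early removal, POD 5-7, POD 12-14 and weekly visits) is the CDC/NHSN decision recorded by the blinded NP or PA after other staff have removed the dressing.
- Where only an unblinded clinician saw the wound, or a possible SSI is first reported at the POD 30 contact, the blinded NP or PA decides from notes with arm details masked.
- A field on the assessment form records who assessed the wound and whether that person was blinded.

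The rule settles only which diagnosis is counted; clinical care by the treating team is unchanged.

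The cost is protocol wording, one form field, some scheduling effort to have the blinded NP or PA available at unscheduled visits, and staff time to mask notes. It extends the sequence already written under Postoperative wound management and needs no new assessor. A decision from masked notes is weaker than an examination, so it should remain the fallback.
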